8.0 CORRELATIVE STUDIES

8.1 FFPE

Optional submission of tumor tissue, submitted as Formalin Fixed Paraffin Embedded (FFPE) tissue on 12 glass slides will be submitted to the study coordinating site within 28 days of Course 1 Day 1. Slides will be identified by study participant number.

8.2 Immunohistochemistry

Immunohistochemistry will be performed for biological markers of mTOR pathway activation, including phosphorylated S6^{235/236}, phosphorylated S6^{240/244}, phosphorylated

PRAS40 (pT246), phosphorylated 4EBP1, phosphorylated P70^{S6K}, and PTEN expression.

8.2.1 Intensity of immunohistochemistry staining for each biomarker will be scored as Negative (-); weakly positive (+); moderately positive (++) and strongly positive (+++).

8.2.2 Results of intensity of immunohistochemistry staining will be described and correlated with tumor response to Everolimus.

Send slides to the address below and clearly label package as CRAD001 study. Also, send an e-mail notification at time of shipping to the Study PI <[contact]>, study coordinator <[contact]>, and [name] <[contact]> including tracking number. Central review is not required prior to starting therapy.

[name]
Department of Pathology
Children's Medical Center – Dallas
[name]
[name]

8.2.3 Immunohistochemistry will be performed on FFPE tumor tissue on slides for H3.K27me3 according to established methods. Based upon staining, tumors will be classified as Ependymoma Group A (negative – light staining) or Ependymoma Group B (positive staining). Descriptive results will be reported in the manuscript.

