1.6 Examination of H3.K27me3 Expression in Ependymoma

Since 2011, several studies have been published that have segregated pediatric posterior fossa ependymomas by DNA methylation-based methods into subtypes labeled Group A and Group B.³¹ Group A ependymomas occur more frequently among children and males and have a poor survival; whereas Group B ependymomas occur more frequently among adults, have equal percentages of males and females, and have a relatively good survival.³¹ Panawalker *et al.* recently identified expression of H3.K27me3 by immunohistochemistry as correlating very closely with DNA methylation-based subtyping with very high sensitivity (99%) and specificity (100%) in the ability to distinguish Group A posterior fossa ependymoma from Group B posterior fossa ependymoma.³² Furthermore, this study and others have determined that low levels of expression of H3.K27me3 by immunohistochemistry are associated with poor event free and overall survival for children with ependymoma.³²⁻³⁴

For tumors from subjects enrolled on this protocol, we will perform immunohistochemistry for H3.K27me3 on existing and available FFPE slides on enrolled subjects (and controls) according to established methods to determine ependymoma subtype (either Group A or Group B). Given the population of patients with recurrent ependymoma enrolled on this study, we predict that the majority of enrolled tumors will be classified as Group A. A description of the results will be reported in the manuscript.

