3.1 Inclusion Criteria

- 3.1.1 Diagnosis and Age: Ependymoma (WHO grade II) or Anaplastic Ependymoma (WHO grade III) that has relapsed or become refractory to standard therapy. Patients must have had histologic verification of their malignancy at original diagnosis or time of recurrence. Age must be \geq 2 years and \leq 21 years of age at study entry.
- 3.1.2 Performance status: Lansky \geq 50% for patients \leq 10 years of age or Karnofsky \geq 50% for patients $>$ 10 years of age.
- 3.1.3 Adequate bone marrow function as shown by: ANC \geq 1000/mm³, platelets \geq 100,000/mm³ and hemoglobin $>$ 9.0 g/dL. Note: these lab parameters must be transfusion-independent
- 3.1.4 Adequate liver function as shown by:
 - 3.1.4.1 Total serum bilirubin \leq 2.0 mg/dL.
 - 3.1.4.2 ALT and AST \leq 2.5x ULN
 - 3.1.4.3 INR \leq 2.
- 3.1.5 Adequate renal function: serum creatinine \leq 1.5x ULN.
- 3.1.6 Fasting serum cholesterol \leq 300 mg/dL OR \leq 7.75 mmol/L AND fasting triglycerides \leq 2.5x ULN. NOTE: In case one or both of these thresholds are exceeded, the patient can only be included after initiation of appropriate lipid lowering medication.
- 3.1.7 Signed informed consent obtained prior to any screening procedures.

- 3.1.8 Patients must have measurable residual disease, defined as tumor that is measurable in two diameters on MRI. Diffuse leptomeningeal disease is not considered measurable.
- 3.1.9 Prior Therapy: Patients must have fully recovered from the acute toxic effects of all prior chemotherapy, immunotherapy, and radiotherapy prior to participating in this trial.
 - 3.1.9.1 No prior myelosuppressive chemotherapy for at least 21 days prior to study enrollment.
 - 3.1.9.2 Must not have received craniospinal radiation therapy within 24 weeks prior to study entry and no involved field radiation therapy for 12 weeks prior to study enrollment.
 - 3.1.9.3 If patients received prior monoclonal antibody treatment, at least three half-lives must be elapsed by the time of treatment initiation.
 - 3.1.9.4 No investigational drugs for 4 weeks prior to study enrollment.
 - 3.1.9.5 No prior therapy with mTOR inhibitors (including sirolimus, temsirolimus or everolimus).

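### The H3.K27me3 Group A/B label is not limited to posterior fossa tumours, so any other primary with tissue gets a label that the cited evidence does not support

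*Combined protocol and SAP*

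**What the plan says.** Section 1.6 explains that methylation studies have "segregated pediatric posterior fossa ependymomas by DNA methylation-based methods into subtypes labeled Group A and Group B". It then credits H3.K27me3 immunohistochemistry with a sensitivity of 99% and a specificity of 100% for one task, the "ability to distinguish Group A posterior fossa ependymoma from Group B posterior fossa ependymoma".

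The same section plans to stain whatever slides exist for enrolled subjects and to assign each tumour one of the two subtypes. It predicts that most enrolled tumours will fall in Group A. Section 8.2.3 gives the working rule: "Based upon staining, tumors will be classified as Ependymoma Group A" when staining is negative or light, and as Group B when it is positive. Neither section names a site restriction, a third category or a not-applicable outcome. Both promise a descriptive report in the manuscript.

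Section 3.1.1 admits "Ependymoma (WHO grade II) or Anaplastic Ependymoma (WHO grade III) that has relapsed or become refractory to standard therapy", with no anatomical criterion. Section 3.1.10 requires MRI of both brain and spine. Under sections 3.1.11 and 8.1, tissue is submitted only if available and submission is optional.

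**The concern.** The rule is wider than the evidence offered for it. The split and the accuracy figures belong to posterior fossa tumours, whereas the rule applies to any enrolled tumour with slides. A supratentorial or spinal primary that is stained has to be called A or B, because the rule has no other outcome.

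What is at stake is how the manuscript's subtype description can be read. The natural summary is the share of tumours in Group A, which is also the quantity that section 1.6 predicts. If other primaries are included, that share combines labels backed by the 99% and 100% figures with labels backed by nothing in the plan, and a reader could not separate them unless primary site were also shown.

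**Working it through.** The plan gives no figure to reproduce here. The check is mainly a comparison of scope, followed by an illustration of size.

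**Scope, section against section**

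| Element | Where | Scope stated |
|---|---|---|
| Definition of Groups A and B | 1.6 | Posterior fossa |
| Accuracy of the stain (99%, 100%) | 1.6 | Posterior fossa A versus posterior fossa B |
| Link between low H3.K27me3 and poor survival | 1.6 | Childhood ependymoma generally |
| Tumours to be stained and labelled | 1.6 | Enrolled subjects with slides, any site |
| Classification rule | 8.2.3 | Tumours, any site, two outcomes |
| Eligibility | 3.1.1 | Grade II or III ependymoma, any site |

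The first two rows are narrower than the last three. The third row reaches beyond the posterior fossa, but it concerns prognosis. It gives a reason to stain every tumour and no reason to attach an A or B label at other sites. Section 1.3 describes the group's own earlier series as infratentorial, so the protocol does distinguish location elsewhere.

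**How many labels**

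Number of unsupported labels = (tumours stained) × (share with a primary outside the posterior fossa).

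- Tumours stained: at most 18 (section 9.2), fewer if slides are missing.
- Share at other sites: not given. A range of 10% to 40% is assumed for illustration.
- Full accrual, all with tissue: 18 × 0.10 = 1.8 and 18 × 0.40 = 7.2, so about 2 to 7.
- If the study stops after the first stage of 7 patients, all with tissue: 7 × 0.10 = 0.7 and 7 × 0.40 = 2.8, so about 1 to 3.

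**Effect on the Group A share**

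Let m posterior fossa tumours be stained, a of them Group A. Let k other primaries be stained, j of them negative or light. The supported share is a/m. The rule as written reports (a + j)/(m + k).

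With assumed values m = 14, a = 12, k = 4:

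- supported share: 12/14 = 85.7%
- all four others stain positive (j = 0): 12/18 = 66.7%
- all four others stain negative or light (j = 4): 16/18 = 88.9%

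The reported share would move by between −19.0 and +3.2 percentage points in this example, so the shift can go either way. With 18 tumours, one label is worth 1/18 = 5.6 points.

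**The case against.** The strongest reply is that the context supplies the restriction. Section 1.6 introduces the groups as posterior fossa subtypes just before it sets out the staining plan, and section 8.2.3 is a short operational restatement. A pathologist might apply the label only where it belongs. This is plausible, but it is not what the rule says. Section 8.2.3 omits the site and offers two outcomes for all stained tumours, and the prediction in section 1.6 refers to enrolled tumours as a whole.

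A second reply is that nothing depends on the result. This stands. H3.K27me3 is absent from the objectives and endpoints (sections 2.1 to 2.3 and 9.1) and from the analysis plan in 9.3, whose planned correlations name only the mTOR pathway markers. The two-stage decision rule in 9.2 does not use it.

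A third reply is that brain and spine MRI at entry does not show that other primaries will enrol. This also stands. Patients have recurrent or progressive disease, and a posterior fossa primary may have measurable disease elsewhere. The possibility of other primaries rests on the absence of a site criterion in 3.1.1, not on the imaging requirement.

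**Conclusion.** The point holds as a mismatch between a classification rule and the evidence cited for it. Any primary outside the posterior fossa that has tissue would receive an unsupported A or B label, and the Group A share would mix the two kinds. It is a minor point, confined to one exploratory description.

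A reader might infer three stronger things, and the documents do not support them:

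- That every enrolled tumour is labelled. Tissue is optional, so only tumours with slides are.
- That every tumour outside the posterior fossa is misclassified. The documents do not say how the stain behaves at other sites. They show only that the cited evidence does not cover them.
- That the prediction of a Group A majority must fail. It is an aggregate expectation and could hold even at the 40% end of the assumed range. With 7 of 18 tumours at other sites, all staining positive, and the remaining 11 all Group A, the share is 11/18 = 61%.

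The count of 2 to 7 rests on an assumed site mix, full accrual and complete tissue. The true number is unknown and could be zero.

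**What to change.** In sections 1.6 and 8.2.3, restrict the A/B label, and the denominator of any Group A share, to tumours whose primary site is the posterior fossa. For other primaries, report the H3.K27me3 staining result without a group label. Tabulate primary site alongside.

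Take primary site from the medical and surgical history already collected at screening (section 5.1.2) or from the pathology record. The enrolment MRI is not a safe source: it shows current disease, which may be a metastatic site, while the slides may come from the original diagnosis or a later operation.

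The cost is about one sentence in each section and one recorded item. No staining data are lost. The downside is that fewer tumours enter the A/B table.

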9.0 STATISTICAL CONSIDERATIONS

9.1 Study Design/Study Endpoints

The study is a prospective single-arm multi-center phase II study that determines the objective response rate following treatment with everolimus for children with recurrent or progressive ependymomas. Given the relatively small study sample size, descriptive statistics will be used to report the results of the study.

Study endpoints include the following:

- Objective Response Rate = Complete Response Rate + Partial Response Rate + Prolonged Stable Disease Rate.
- Duration of Response
- Progression Free Survival
- Overall Survival
- Dose-limiting toxicities
- Biological markers of mTOR pathway activation, including phosphorylated S6^{235/236}, phosphorylated S6^{240/244}, phosphorylated PRAS40 (pT246), phosphorylated 4EBP1, phosphorylated P70^{S6K}, and PTEN expression.

9.2 Sample Size and Accrual

Simon's two-stage optimal design³⁵ is used to compute the number of patients to be recruited for this phase II trial. The null hypothesis that the true objective response rate (ORR) is 10% will be tested against a one-sided alternative. In the first stage, 7 patients will be accrued. If there is no ORR seen in these 7 patients, the study will be stopped.

Otherwise, 11 additional patients will be accrued for a total of 18 patients. The null hypothesis will be rejected if 4 or more ORRs are observed in 18 patients. This design yields a type I error rate of 10% and power of 80% when the true ORR is 30%. It is expected that the accrual will be completed in 2 years since 9 patients are expected to be recruited in a year.

9.3 Data Analyses Plans

Objective response rate and the corresponding 95% confidence interval will be estimated using the exact binomial method. Kaplan-Meier method will be used to estimate the duration of response, progression free survival (PFS) and event free survival (EFS) following treatment with everolimus for children with recurrent or progressive ependymomas. The corresponding 95% confidence interval will be computed using Greenwood's formula. Safety and tolerability of everolimus will be estimated using exact binomial method. Exploratory analysis will be conducted to investigate the correlation between response rate and biological markers of mTOR pathway activation, including phosphorylated S6^{235/236}, phosphorylated S6^{240/244}, phosphorylated PRAS40 (pT246), phosphorylated 4EBP1, phosphorylated P70^{S6K}, and PTEN expression.

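### The planned 95% exact binomial interval does not match the one-sided 10% two-stage test, so a trial that rejects with 4 or 5 of 18 reports an interval containing 10%; the raw rate is also slightly low

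*Combined protocol and SAP*

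**What the plan says.** Section 9.2 adopts "Simon's two-stage optimal design" and frames a formal test: "The null hypothesis that the true objective response rate (ORR) is 10% will be tested against a one-sided alternative". The design limits are 10% type I error and 80% power at a true ORR of 30%. Stage 1 has 7 patients, with this futility rule: "If there is no ORR seen in these 7 patients, the study will be stopped". With at least one response, enrolment goes on by 11 more to reach 18. The final decision rule is a count: "The null hypothesis will be rejected if 4 or more ORRs are observed in 18 patients".

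The analysis plan in section 9.3 gives the primary endpoint one sentence: "Objective response rate and the corresponding 95% confidence interval will be estimated using the exact binomial method". The Statistical Methodology entry of the Study Summary repeats it. Neither place mentions the two stages, a p-value, or a confidence level tied to the test. Neither says how to read a result in which the test rejects and the interval still contains 10%. Section 9.1 adds that, because the sample is small, reporting will be descriptive.

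**The concern.** The test allows 10% error in one tail. A two-sided 95% interval allows 2.5% in that tail. At the smallest rejecting counts the report would state that 10% is rejected and, beside it, give an interval that includes 10%. The plan offers no agreed way to read the two together, so that choice would be made after the data are seen.

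The second issue is separate. The exact binomial method treats 18 patients as one fixed sample, but a trial reaches 18 only if stage 1 had at least one response. The ordinary proportion and its limits ignore that condition. The effect is to understate activity, most visibly when few responses are seen.

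**Working it through.** **Inputs.** From section 9.2: null rate 0.10, target 0.30, stage 1 size 7, stop at 0, total 18, reject at 4 or more. From section 9.3: a 95% exact binomial interval. Sidedness is not stated; I take it as two-sided Clopper-Pearson.

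**1. Reproduce the design.** P(reject | p) = sum over x = 1 to 7 of b(x; 7, p) × P(X2 ≥ 4 − x; 11, p).
- p = 0.10: 0.3720×0.0896 + 0.1240×0.3026 + 0.0230×0.6862 + 0.0027 = 0.0893.
- p = 0.30: 0.2471×0.6873 + 0.3177×0.8870 + 0.2269×0.9802 + 0.1260 = 0.8000.

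A search under the stated limits returns exactly this design (0/7, 3/18) as Simon's optimal. The plan's 10% is the limit; the attained type I error is 8.9%.

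**2. Intervals at the rejecting counts.** Planned limits solve P(X ≥ s; 18, p) = 0.025 and P(X ≤ s; 18, p) = 0.025. Two-stage limits solve the same equations over the two-stage sample space, with the stop at 0/7 ordered lowest. The two-stage p-value is P(continue and S ≥ s) at p = 0.10.

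| Result | Raw | Planned 95% | Two-stage 95% | Plain 80% | Two-stage one-sided 90% lower bound | Two-stage p |
|---|---|---|---|---|---|---|
| 4/18 | 22.2% | 6.4-47.6% | 6.6-49.1% | 10.06-39.6% | 10.4% | 0.089 |
| 5/18 | 27.8% | 9.7-53.5% | 9.8-54.0% | 14.2-45.5% | 14.4% | 0.027 |
| 6/18 | 33.3% | 13.3-59.0% | 13.4-59.2% | 18.5-51.2% | 18.6% | 0.006 |

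The planned interval first excludes 10% at 6 responses.

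**3. Which feature causes the mismatch.** Change one thing at a time. Adjusting for the two stages and keeping 95% leaves lower limits of 6.6% and 9.8%, so 10% is still inside. Keeping the plain binomial method and using 10% per tail gives 10.06% and 14.2%, so 10% is outside. The level alone accounts for it.

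**4. How often it would occur.** At a true 30%, P(4) + P(5) = 0.1500 + 0.1908 = 0.3408, and 0.3408 / 0.8000 = 43% of rejections. At a true 20%, 0.3347 / 0.4652 = 72%.

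**5. Bias of the raw rate.** A stopped trial contributes 0/7, and E[X1; continue] = 7p. So E[raw] = {7p + 11p[1 − (1 − p)^7]} / 18, and the bias is −(11/18) × p × (1 − p)^7.
- p = 0.10: −0.6111 × 0.10 × 0.4783 = −2.9 points.
- p = 0.20: −0.6111 × 0.20 × 0.2097 = −2.6 points.
- p = 0.30: −0.6111 × 0.30 × 0.0824 = −1.5 points.

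**6. UMVUE.** This is the average of x/7 over x ≥ 1, with weights C(7, x) × C(11, s − x). At s = 4 the weights for x = 1 to 4 are 1155, 1155, 385 and 35, total 2730. The estimate is (1155 + 2310 + 1155 + 140) / (7 × 2730) = 680 / 2730 = 24.9%, against a raw 22.2%. At s = 5 it is 2380 / 8106 = 29.4%, against 27.8%.

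**7. Upper limit after few responses.** At 1/18 the planned limit solves (1 − p)^18 + 18p(1 − p)^17 = 0.025, giving 27.3%. The two-stage limit solves (1 − p)^7 + 7p(1 − p)^17 = 0.025, giving 41.1%. The first excludes the 30% target; the second does not. At 2/18 the limits are 34.7% and 42.1%.

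**8. Coverage of the planned interval under the two-stage design.** It is 99.4% at a true 10% and 97.4% at 30%. The minimum over true rates from 1% to 90% is about 95.0%.

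**The case against.** The strongest defence is that the interval was never meant as a test. The decision rests on a count, and section 9.1 calls the reporting descriptive. A 95% interval beside a one-sided 10% screening test answers a different question. Its inclusion of 10% at 4/18 fairly shows modest evidence (p = 0.089). This stands: the pairing is not an error in itself, and no go/no-go decision changes. What remains is that the plan does not say how the two relate.

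A reader might infer three stronger things that the documents do not support.
- **That the two-stage design causes the mismatch.** Step 3 shows that it does not.
- **That the planned interval is invalid.** Its coverage does not fall materially below 95%. The 99.4% at a true 10% is ordinary discreteness; a fixed sample of 18 gives 99.4% there too.
- **That an 80% interval should replace the 95% one as the headline.** That would make a borderline result in 18 patients look firmer than it is.

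It is also fair to say that the bias is small against the sampling error (root mean squared error, RMSE, of the raw rate 8.7 to 13.2 points) and cannot create a false claim of activity. The UMVUE is not uniformly better. Its RMSE is 10.1 points against 8.7 at a true 10%, 12.0 against 12.2 at 20%, and 12.4 against 13.2 at 30%. It also turns 1/18 into 14.3%. These are reasons to show it beside the raw rate, not in its place.

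**Conclusion.** The point holds as a modest reporting gap. The level of the planned interval differs from that of the test, so 4/18 and 5/18 reject 10% while the interval contains it. Separately, the single-sample method understates the rate by 1.5 to 2.9 points at true rates of 10-30% and gives low upper limits after few responses. The second effect matters most for a negative trial: at 1/18 the planned interval rules out the 30% target and the design-based one does not.

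Sample size, stopping rule and decision rule are unaffected, and the planned interval errs on the conservative side.

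The conclusion assumes a two-sided Clopper-Pearson interval and the raw proportion as the estimate. Both are the ordinary reading of section 9.3, but neither is spelled out. If a one-sided 95% lower bound were meant, 4/18 would still include 10% (8.0%) and 5/18 would not (11.6%). The design-based limits assume that the stage 1 stop ranks below every completed trial; the 41.1% at 1/18 depends on that ordering. The calculations also assume that exactly 7 and 18 patients are analysed.

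**What to change.** In section 9.3 and the Study Summary:
- State that the count rule in section 9.2 decides the test and that the interval describes precision.
- Beside the raw rate, report the UMVUE and the two-stage exact p-value (0.089 at 4/18, 0.027 at 5/18).
- Compute the 95% interval by the two-stage exact method, name the ordering used, and keep this interval as the headline (6.6-49.1% at 4/18).
- Add a design-based one-sided 90% lower bound, which matches the level of the test (10.4% at 4/18, 14.4% at 5/18).

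The cost is a few sentences and a few lines of code. The 95% interval becomes slightly wider: at 4/18, 49.1 − 6.6 = 42.5 points against 47.6 − 6.4 = 41.2. It will still contain 10% at 4 and 5 responses, which is why the first and last items are needed. The UMVUE brings a somewhat larger mean squared error if the true rate is 10%.

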10.0 STUDY MANAGEMENT

10.1 Conflict of Interest

Any investigator who has a conflict of interest with this study (patent ownership, royalties, or financial gain greater than the minimum allowable by their institution, etc.) must have the conflict reviewed by the Conflict of Interest Office at their respective institution. All investigators will follow the University conflict of interest policy.

